## 10.2.4 Secondary outcome analysis

Secondary outcomes will be analysed following the principles outlined in Section 10.2.1 (unless otherwise stated). Brief details of the analyses of the secondary outcomes are given below. Detailed specification of these analyses will be given in the SAP.

#### Desirability of Outcome Ranking (DOOR)

Patients will be categorised according to the worst outcome they experience over the 6 months follow up period using a four-level ordinal classification. The four levels will be  $C_1$  = No treatment failure,  $C_2$  = Treatment failure (as for the primary outcome),  $C_3$  = Treatment failure associated with sepsis and  $C_4$  = Treatment failure associated with death.

The DOOR will be analysed using a mixed effect proportional odds model with group allocation, the stratification factors and other prognostic baseline covariates included as fixed effects, with random intercepts for recruitment site. The estimated conditional odds ratio for allocation and two-sided 95% CI and p-value from this model will be reported. For i = 2, 3 and 4, risk ratios ( $Pr(Y \ge C_i | Z = Intervention, X)/Pr(Y \ge C_i | Z = Control, X)$ ) and absolute risk reductions ( $Pr(Y \ge C_i | Z = Intervention, X) - Pr(Y \ge C_i | Z = Control, X)$ ) based on the fitted model, will also be reported (with appropriate 95% confidence intervals) at various representative covariate patterns X (i.e. marginal effects at

representative values). The fitted model will also be used to compute average marginal effects of allocation on both the risk ratio and risk difference scales.

The extent to which the effect of allocation meets the proportional odds assumption will be assessed using both Brant and likelihood ratio tests (the likelihood ratio test will compare a proportional odds model with a less restrictive partial proportional odds model that allows the effect of allocation to differ across each of the three possible binary groupings of the outcome). If either of these tests suggest the effect of allocation deviates substantially from the proportional odds assumption, then the partial proportional odds model will be fitted (with cluster robust standard errors), and the three estimated odds ratios for allocation (one for each of the three possible binary groupings of the outcome) will be reported together with appropriate 95% confidence intervals and p-values [27].

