## 10 STATISTICS AND DATA ANALYSIS

## 10.1 Sample size calculation

The primary outcome for this study is treatment failure. Using an estimated proportion of treatment failure in the standard treatment group of  $\geq$  50% over the 180 days of follow up, an effective sample size of 1048 patients (524 per arm) obtains 90% power to detect a 10% (absolute) reduction in incidence of the clinical outcome in a two-sided test of size 5%. Assuming 10% attrition 1166 patients (583 per arm) are required. The sample size calculation was carried out using Stata version 16.0.

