#### Number of episodes of treatment failure

The total number of episodes of treatment failure during the 180 days following randomisation will be reported descriptively by randomised group and overall. For analysis, death within 180 days following randomisation will be coded as the "worst"/"highest" outcome (i.e. death will be ranked worse than any number of treatment failure episodes without death). This outcome and its empirical cumulative distribution function will be plotted by randomised group and overall. Total number of episodes of treatment failure (with death coded as the worst/highest outcome) will be compared using a proportional odds model, with fixed effects for allocation, the stratification factors and other prognostic baseline covariates, and random intercepts for study recruitment site. This model will be used to derive marginal effects (on both the risk ratio and risk difference scales) conditional on pre-specified values of interest for the fixed effects (on both the risk ratio and risk ratio and risk difference scales) will also be reported together with appropriate 95% confidence intervals for various relevant outcomes/cut-offs.

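### The DOOR risk ratio for failure with death is derived from one common odds ratio unless a test rejects, so a treatment that reduces failure but not fatal failure can appear to reduce both

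*Protocol*

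**What the plan says.** Protocol 10.2.4, Desirability of Outcome Ranking (DOOR), defines four ordered levels: no failure (C1), treatment failure (C2), failure with sepsis (C3) and failure with death (C4). Section 3.5 adds that the sepsis or death must fall within 5 days of antibiotics being started or changed.

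The analysis is a mixed proportional odds model with one coefficient for allocation. Risk ratios and absolute differences for being at or above C2, C3 and C4 are, the text says, "based on the fitted model, will also be reported (with appropriate 95% confidence intervals) at various representative covariate patterns X". Average marginal effects come from the same model.

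The proportional odds assumption for allocation is checked with a Brant test and a likelihood ratio test. The rule is: "If either of these tests suggest the effect of allocation deviates substantially from the proportional odds assumption, then the partial proportional odds model" is fitted and three cut-specific odds ratios are given with intervals and p-values. No significance level is stated. The text does not say what becomes of the proportional-odds risk ratios after a switch.

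All-cause mortality has its own proportional hazards analysis in 10.2.4. Several other secondary outcomes put death at the top of an ordinal scale. For the number of failure episodes, for example, "death will be ranked worse than any number of treatment failure episodes without death".

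**The concern.** With one allocation coefficient, the C4 risk ratio carries almost no information about C4. It restates the common odds ratio at the C4 baseline risk, and its interval excludes 1 essentially whenever the interval for the common odds ratio does. The precision comes from the large number of patients who fail at all, not from the few who fail and die.

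The only safeguard is a test of proportional odds. When it does not reject, the effect on fatal failure is in practice taken to equal the effect on failure. With few C4 events, the test can easily miss a real difference between those two effects.

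At stake is what the trial says about its worst DOOR level. A reader who sees a C4 risk ratio near 0.7 with an interval below 1 will take it as evidence that longer treatment prevents fatal failure, even if the C4 rates in the two arms are the same.

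**Working it through.** **Inputs from Protocol 10.1.** Control failure is at least "50% over the 180 days of follow up"; 50% is used here. The design aims to "detect a 10% (absolute) reduction in incidence of the clinical outcome", that is 50% v 40%. On size, "an effective sample size of 1048 patients (524 per arm) obtains 90% power" in a "two-sided test of size 5"%. On recruitment, "Assuming 10% attrition 1166 patients (583 per arm) are required".

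**Reproducing the plan's figure.** n per arm = [z(0.975)·√(2·0.45·0.55) + z(0.90)·√(0.5·0.5 + 0.4·0.6)]² / 0.10² = (1.960 × 0.7036 + 1.2816 × 0.7000)² / 0.01 = 518.1, so 519. The stated 524 gives 90.3% power. Then 524 / 0.9 = 582.2, so 583 per arm and 1166 in total. The design is sound. No power or error rate is given for DOOR.

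**Inputs assumed.** The protocol gives no C3 or C4 rate. Section 1 cites 11.3% deaths in a UK cohort. C4 should be rarer because of the 5-day window, so C4 is taken as 3%, 5% or 8%. Each test is run at 5%. Covariates and site effects are left out.

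**Mechanism.** The model is logit Pr(Y ≥ Ck) = a_k + b·Z, with the same b for k = 2, 3, 4. The design effect at C2 is (0.4/0.6)/(0.5/0.5) = 0.667. If that ratio is applied at a 5% C4 rate, the odds are 0.0526 × 0.667 = 0.0351 and the risk is 0.0339. The risk ratio is 0.0339/0.05 = 0.68, whatever happened to the deaths.

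**Where the information lies.** Expected failures are 262 v 210. At C4 = 5% there are about 26 events per arm.
- SE of the log odds ratio at C2: √(1/262 + 1/262 + 1/209.6 + 1/314.4) = 0.125
- SE at C4: √[2 × (1/26.2 + 1/497.8)] = 0.28

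The C2 cut carries roughly five times the information.

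**True cut-specific odds ratios, with C4 = 5% in both arms:**
- Sepsis falls in line with non-fatal failure (split 2:1 between C2 and C3). C2/C3/C4 are 30/15/5% v 23.3/11.7/5%. The odds ratios are 0.667, (0.1667/0.8333)/(0.20/0.80) = 0.80, and 1.00.
- Only ordinary failure falls (C3 = 10%). C2/C3/C4 are 35/10/5% v 25/10/5%. The odds ratios are 0.667, 1.00 and 1.00.

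**Simulation.** Each scenario used 524 per arm and 800 to 2000 trials. A false benefit means that proportional odds is retained and the upper 95% limit of the model-based C4 risk ratio is below 1.

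| True state | Proportional odds rejected (C4 3/5/8%) | False C4 benefit (C4 3/5/8%) |
|---|---|---|
| Sepsis falls in line, C4 equal | 20/29/37% | 68/61/50% |
| Only ordinary failure falls, C3 10% | 55/60/73% | 35/30/20% |
| Only ordinary failure falls, C3 20% | 86/89/96% | 9/7/3% |
| Sepsis in line, C4 truly up 30% | 46/65/89% | 42/25/9% |

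Repeat runs of the first row gave 47–71% across the three C4 rates. Its median C4 risk ratio is 0.71–0.73, against a truth of 1.00. The Brant test adds at most 0.3 percentage points to the likelihood ratio test in that case.

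**Two reference points.** Under a full null the model shows a C4 benefit in 2.2% of trials, so the excess comes from carrying one odds ratio across levels. With equal C4 rates, a directly estimated C4 contrast gives a false reduction in 1.6–3.2%, close to the nominal 2.5%.

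**After a rejection.** If the proportional-odds C4 risk ratio were still printed, its interval would lie below 1 in 61–78% of trials when only ordinary failure falls.

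**The case against.** The strongest replies are these.

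- **The tests are not uniformly weak.** If only ordinary failure falls, they reject in 55–96% of trials. This stands, and it is why that case gives 3–35% rather than 50–70%. A reader might infer that a false death-level finding is certain or always likely; no scenario shows that.
- **Harm is not usually reported as benefit.** A reader might infer that a rise in fatal failure would normally appear as a reduction. With a true 30% rise the figure is about 10–40%, below half throughout.
- **The protocol plans no formal test at C4.** P-values attach to the common odds ratio and the fallback odds ratios; the level-specific risk ratios have intervals only. This is correct, but an interval excluding 1 will be read the same way.
- **Mortality has its own model, and raw C4 counts would normally be tabulated.** Both help. The mortality analysis is free of the artefact, but it covers all deaths to 180 days and does not correct a printed C4 risk ratio.
- **Detail is left to the SAP.** The test threshold may be there. The protocol itself, however, fixes the source of the C4 risk ratio and makes the cut-specific odds ratios conditional.
- **Other outcomes.** A reader might infer the same error for nights in hospital, failure episodes, ventilation and renal replacement, which rank death worst and state no check. Those paragraphs promise effects at relevant cut-offs but name none for death, so the point reaches them only if a death cut-off is reported.

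**Conclusion.** The concern holds for the DOOR analysis in this form: following the text can give a C4 risk ratio with an interval below 1 when treatment does nothing at C4, far more often than the nominal 2.5% in most of the cases examined. The rate is about 50–70% if sepsis falls in line with non-fatal failure and about 3–35% if only ordinary failure falls (C3 10–20%). If C4 truly rises by 30%, a false benefit appears in about 10–40%.

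These figures rest on assumed C3 and C4 rates, tests at 5%, and a model without covariates or site effects. The direction does not depend on them, because it follows from using one coefficient for all three cuts. That the text leaves the fate of the risk ratios open after a rejection is a separate gap.

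The primary analysis is unaffected. This concerns derived quantities within one secondary outcome, and it should be changed because they bear on death and the change is cheap.

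**What to change.** In Protocol 10.2.4 (DOOR), and in the SAP to match:

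- Keep the common odds ratio as the single DOOR summary and test.
- Always report odds ratios, risk ratios and risk differences at C2, C3 and C4, with intervals, from the partial proportional odds model or from separate mixed logistic models with the same covariates. Do this whatever the Brant or likelihood ratio result.
- State that C3 and C4 effects are not derived from the common odds ratio.
- If a death cut-off is reported for nights in hospital, failure episodes, days of ventilation or days of renal replacement, estimate it directly in the same way.

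The cost is wording and three extra model outputs, with no new data. The interval at C4 will be wider. With 26.2 expected events per arm, the SE of the log risk ratio is √[2 × (1/26.2 − 1/524)] = 0.27, so a true ratio of 1.00 would have a 95% interval of about 0.59 to 1.70. That width reflects what the trial can say about fatal failure.

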#### EQ-5D-5L

Participants will complete the EQ-5D-5L at baseline, and at days 30, 90 and 180 post-randomisation. Analysis of EQ-5D data will be part of the health economics analysis and will be described in the Health Economics Analysis Plan (HEAP). For the statistical analysis, descriptive summaries of the EQ-5D data at each time point will be given by randomised group and overall.

#### Source control procedures

The number, incidence and type of source control procedures occurring over the 180 days following randomisation will be reported descriptively by randomised group. The total number of source control procedures of different types (radiological, surgical) and source control procedures of any type occurring in each randomised group will be compared using a proportional odds model, with fixed effects for allocation, the stratification factors and other prognostic baseline covariates, and random intercepts for study recruitment site. This model will be used to derive the difference in mean number of source control procedures in each group, conditional on pre-specified representative values of the fixed effect covariates, as well marginal effects (on both the risk ratio and risk difference scales)

The EXTEND Trial protocol ISRCTN no. 72819021

conditional on pre-specified representative values of the fixed effect covariates (e.g. Pr(Y > 0 |Intervention, X)/Pr(Y > 0 | Control, X) for covariates X). Average marginal effects (on both the risk ratio and risk difference scales) will also be reported together with appropriate 95% confidence intervals for various relevant outcomes/cut-offs.

#### Length of hospital stay

The length of initial hospital stay (i.e. time to first discharge following randomisation) will be analysed using competing risk regression methods. For this analysis, the day of randomisation will be treated as day zero and the day of discharge will be the event of primary interest, with death treated as a competing event. Both discharge and death will be considered absorbing states. Time to discharge will be analysed using both cause specific, and sub-distribution hazards models, with fixed effects for allocation, the stratification factors and other prognostic baseline covariates, and shared frailties for study recruitment site. The former will be used to estimate the effect of the intervention on the instantaneous rate of discharge among those that are event free, and the latter to estimate the effect of the intervention on the cumulative incidence of discharge (conditional on pre-specified values of interest for the fixed effect covariates).

#### Days/Nights in hospital

The total number of nights spent in hospital during the 180 days following randomisation, proportion of total follow up time in hospital and mortality will be reported descriptively by randomised group and overall. For analysis, death within 180 days following randomisation will be coded as the "worst"/"highest" outcome (i.e. death will be ranked worse than any number of nights in hospital without death). This outcome and its empirical cumulative distribution function will be plotted by randomised group and overall. Total number of nights in hospital (with death coded as the worst/highest outcome) will be compared using a proportional odds model, with fixed effects for allocation, the stratification factors and other prognostic baseline covariates, and random intercepts for study recruitment site. This model will be used to derive marginal effects (on both the risk ratio and risk difference scales) conditional on pre-specified representative values of the fixed effect covariates (e.g. Pr(Y > 28 | Intervention, X)/Pr(Y > 28 | Control, X) for covariates X). Average marginal effects (on both the risk ratio and risk difference scales) will also be reported together with appropriate 95% confidence intervals for various relevant outcomes/cut-offs.

#### Days of anti-microbial therapy

The total number of days of anti-microbial therapy (inpatient, outpatient and overall) during the 180 days following randomisation, proportion of total follow up time on anti-microbial therapy, and mortality will be reported descriptively by randomised group and overall. For analysis, death whilst still receiving

antibiotics will be coded as the "worst"/"highest" outcome (i.e. death will be ranked worse than any number of days of antimicrobial therapy without death). This outcome and its empirical cumulative distribution function will be plotted by randomised group and overall. Total number of days on antimicrobial therapy (with death coded as the worst/highest outcome) will be compared using a proportional odds model, with fixed effects for allocation, the stratification factors and other prognostic baseline covariates, and random intercepts for study recruitment site. This model will be used to derive marginal effects (on both the risk ratio and risk difference scales) conditional on pre-specified representative values of the fixed effect covariates (e.g. Pr(Y > 28 | Intervention, X)/Pr(Y > 28 | Control, X) for covariates X). Average marginal effects (on both the risk ratio and risk difference scales) will also be reported together with appropriate 95% confidence intervals for various relevant outcomes/cut-offs.

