
#### 2 RATIONALE

The cIAI feasibility trial and a survey of clinicians showed there is equipoise with regards to this issue and a desire to see good evidence on this. Our UK data suggests that current practice results in unacceptably high rates of cIAI relapse and extra-abdominal infection. As a guiding rule, shorter antibiotic durations are important to combat antimicrobial resistance, but this is not true when these shorter courses need repeating and result in more days in hospital. Optimal care for patients should be our primary concern. The impact of the proposed EXTEND trial, which is studying fixed-extendedduration antibiotics in patients with complicated intra-abdominal infection, will be to improve patient outcomes by providing clinicians with reliable evidence to support them in making the best treatment choices for their patients. If the longer duration strategy is more effective than standard treatment, it is likely to offer direct benefits to the NHS in terms of costs. The literature supports this as when efficacy of antibiotic therapy for cIAI increases, cost savings have been demonstrated. Cost savings included shorter hospital stays and an increase in Quality Adjusted Life Years (QALYs) [20,21]. Reductions in cIAI relapse will also reduce the use of radiological and surgical NHS resources.

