## 7.2.1 Method of implementing the randomisation/allocation sequence

Randomisation will occur within the first 10 days of antibiotic treatment for cIAI, and will be implemented using a web-based system designed and developed by the data management team at YTU. This system will be accessed by clinical research staff involved in patient recruitment at recruiting sites (as detailed in the site delegation log) and will be accessible 24 hours a day and 7 days a week. Prior to randomisation, research staff at recruiting sites will be required to enter the following key information; participant identification number, date of birth, participant contact details (to facilitate follow up), confirmation that the participant meets each of the eligibility criteria and the information required for stratification. The allocation sequences (one for each stratum) will be designed by the trial statistician. The actual sequences embedded in the randomisation system will be generated by a separate YTU statistician independent of the TMG, using a random number seed that will be concealed from all members of the trial team for the duration of the trial. Following randomisation, the research team at the site where the randomisation took place (including the PI, research nurses and pharmacists) will be notified of the treatment allocation by email. Each time a patient is randomised, the CI and central trial management team at YTU will also be notified by email.

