## 8.2 Detailed specification of the intervention

The intervention is a strategy of a fixed-extended-duration antibiotic treatment of 28-days. The start of antibiotic therapy is the first day of effective therapy for cIAI treatment, which will generally occur before randomisation, but could be following randomisation if antibiotics given prior to randomisation are ineffective/inactive. The start date of antibiotic treatment will be determined by the patient's clinical team or clinical research team. Examples of antibiotic therapy that are not therapy for cIAI include antibiotic prophylaxis, or treatment for other infections e.g., cystitis. All treatment will be considered effective unless:

1) Antimicrobial resistance is identified on clinical samples collected before randomisation and that resistance is believed to be clinically relevant i.e., antibiotic treatment is changed based on the microbiological evidence of antibiotic resistance. The start date of fixed-extended-duration antibiotic treatment of 28-days will be re-set to day 0 where antibiotic treatment is changed based on pre-randomisation detection of antibiotic resistance. This strategy relates to the fixed-extended-duration treatment only, and the date of randomisation is not changed.

2) Antibiotics are prescribed for prophylaxis e.g., penicillin for splenectomy, elective surgery antibiotic prophylaxis, UTI prophylaxis

3) Antibiotics are prescribed for the treatment for other infections e.g., cystitis, and not effective against cIAI.

4) Antibiotics are oral antibiotics prescribed prior to hospitalisation

5) Antibiotics from a previous course of antibiotics, a previous course is one stopped for 48 hours or more.

The choice of antibiotic and route of administration are therefore selected by the treating clinician. Source control procedures (surgical and radiological) will be carried out as per standard practice.

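### Risk ratios for total antimicrobial days above 28 (and other cut-offs) are read from one proportional odds ratio, which a fixed 28-day course makes implausible and which overstates the contrast in the upper tail

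*Protocol*

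**What the plan says.** Protocol section 10.2.4, Days of anti-microbial therapy, counts days "during the 180 days following randomisation, proportion of total follow up time on anti-microbial therapy" among the summaries, so the clock starts at randomisation. For analysis, death while still on antibiotics is the top category: "death will be ranked worse than any number of days of antimicrobial therapy without death". The comparison is then fixed: "Total number of days on antimicrobial therapy (with death coded as the worst/highest outcome) will be compared using a proportional odds model". The fitted model supplies marginal risk ratios and risk differences, the worked example being "e.g. Pr(Y > 28 | Intervention, X)/Pr(Y > 28 | Control, X) for covariates X", and average marginal effects with 95% confidence intervals at other relevant cut-offs. Descriptive summaries and the empirical cumulative distribution by arm are also planned. The section names no check of proportionality and no fallback. The DOOR paragraph of section 10.2.4 names both: Brant and likelihood ratio tests, then a partial proportional odds model.

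On the treatment itself, section 8.2 says "The intervention is a strategy of a fixed-extended-duration antibiotic treatment of 28-days" and "The start of antibiotic therapy is the first day of effective therapy for cIAI treatment, which will generally occur before randomisation". Section 7.2.1 adds: "Randomisation will occur within the first 10 days of antibiotic treatment for cIAI". Section 8.3 leaves standard care to clinician judgement. Section 1 reports a UK audit median of 12 days (IQR 7-18).

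**The concern.** A proportional odds model assumes that allocation multiplies the odds of exceeding k days by the same factor for every k. Here allocation sets the outcome directly. It moves most of the 28-day arm above the low cut-offs, while exceeding 28 days after randomisation depends mostly on re-treatment or prolonged treatment, in either arm. A common factor is implausible by design. Good delivery makes the fit worse: the green pilot criterion in section 4.1 asks for more than 10 days' separation between the arms' average durations.

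The tail bears on the stewardship argument. Section 2 grants that shorter courses matter for resistance, but says "this is not true when these shorter courses need repeating and result in more days in hospital". A reader who wants to know whether the 28-day strategy leaves more or fewer patients with long total exposure will look at the contrast above 28 days. If that contrast is read from an odds ratio set mainly by separation below 28 days, its size will be wrong and its interval will be centred on the wrong value.

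**Working it through.** **The plan's own figures.** The antimicrobial-days paragraph states no number to reproduce. The sample size in section 10.1, which supplies the 50% v 40% used below, does reproduce. n per arm = [1.96·√(2·0.45·0.55) + 1.2816·√(0.25 + 0.24)]² / 0.10² = (1.379 + 0.897)² / 0.01 ≈ 519 (538 with continuity correction). The stated 524 per arm gives 90.3% power, and 524/0.9 rounds up to 583 per arm, or 1166.

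**Days left after randomisation.** The 28 days run from the first effective antibiotic day, and randomisation falls within the first 10 treatment days. An exact 28-day course leaves about 28 − 10 = 18 to 28 counted days. By itself it does not give Y > 28.

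**Inputs.**
- From the protocol: standard course of median 12 days, IQR 7-18 (section 1), taken as lognormal; adherent 28-day course within 5 days of target (section 8.4); randomisation on treatment days 1-10 (section 7.2.1); failure 50% v 40% (section 10.1), standing in for re-treatment.
- Assumed, because the protocol gives no figures: adherence 60-100%; repeat courses of median 10-18 days; 4% dying on antibiotics.

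**Method.** Simulate 60,000 patients per arm, fit a cumulative-logit model with allocation only, and compare the simulated (true) Pr(Y > k) with the fitted one.

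**Central case** (80% adherence, 50% v 40%, randomisation on days 1-10). Proportions are control v 28-day arm.

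| Cut-off | True proportions | True OR | True RR (RD) | Model proportions | Model RR (RD) |
|---|---|---|---|---|---|
| >14 | 55.9% v 90.1% | 7.2 | 1.61 (+34 points) | 61.8% v 82.5% | 1.34 (+21) |
| >21 | 38.6% v 68.6% | 3.5 | 1.78 (+30) | 38.4% v 64.6% | 1.68 (+26) |
| >28 | 26.5% v 34.5% | 1.5 | 1.31 (+8) | 18.4% v 39.7% | 2.16 (+21) |
| >42 | 12.8% v 13.9% | 1.1 | 1.09 (+1) | 7.3% v 18.6% | 2.56 (+11) |

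The model columns carry one odds ratio throughout. At >28 it is (0.397/0.603)/(0.184/0.816) ≈ 2.9, and at >14 it is (0.825/0.175)/(0.618/0.382) ≈ 2.9. The true values are (0.345/0.655)/(0.265/0.735) ≈ 1.5 and (0.901/0.099)/(0.559/0.441) ≈ 7.2. The model understates the contrast at low cut-offs and overstates it in the tail. At >28 it also puts the control proportion too low (18.4% against 26.5%).

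**Other scenarios, all at >28.**
- Adherence 60-100%, 50% v 40%: true RR 1.23-1.41, model RR 1.69-2.83.
- Randomisation on days 8-10, 80% adherence, 50% v 40%: true RR 1.12, model RR 1.91.
- Randomisation on days 8-10, 50% v 30%, repeat courses of median 14 days: true RR 0.83 (RD −5 points), model RR 1.42 (RD +10 points).
- All scenarios with re-treatment: true RR 0.69-1.59, model RR 1.18-2.83. The model value was too high in every one.

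**Second simulation.** Section 6.1 requires patients to be on antibiotics until randomisation, which cuts off short control courses. With control courses truncated there, 80% adherence and 50% v 40%, the true OR is about 7 at >14, 1.5 at >28 and 1.1 at >42. At >28 the true RR is 1.32 (RD +9 points) and the model RR about 2.05 (RD +21 points). With repeat courses of median 14 days and adherence 60-95%, the true RR is about 1.1-1.4 and the model RR about 1.5-2.45.

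**The case against.** Several points on the other side stand. This is one of many secondary outcomes. The cut-off of 28 is only an example, and the same one is used for nights in hospital. The empirical distribution by arm would show the tail without a model. Section 10.2.4 leaves detailed specification to an SAP that is not shown and that may add a check. Repeat treatment is addressed more directly by relapse, number of failure episodes and re-admissions. None of this corrects the risk ratios, differences and intervals that the protocol says will be derived from the model.

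Three stronger readings are tempting and not supported.

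- A reader might infer that Y > 28 simply records whether the 28-day course was given. It does not: Y counts days after randomisation, of which an exact course supplies about 18 to 28. The model-based contrast mixes course delivery with later treatment.
- A reader might infer that the model will invent an excess. At the design difference of 50% v 40% the simulations show a real excess above 28 days, which the model exaggerates. Among scenarios with re-treatment, equal or reversed proportions above 28 needed a larger gap, and even that was not always enough: one set of runs at 50% v 30%, with randomisation spread over days 1-10, kept the true RR at 1.03-1.29.
- A reader might call a significant proportional odds result a false positive when the proportions above 28 are equal. The two tests have different nulls. Total days do differ between arms, so rejection is correct, and the protocol plans no separate test at 28.

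**Conclusion.** The concern holds for the derived contrasts. One odds ratio cannot describe a fixed 28-day course against a variable course of median 12 days, and the protocol reads its tail risk ratios and differences from that one odds ratio without the check and fallback it gives DOOR. At the design difference the error is one of size: a true RR of about 1.1-1.4 above 28 days becomes about 1.5-2.45. With a re-treatment reduction of 50% v 30% and late randomisation, the direction can be wrong as well.

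That the odds ratio falls with the cut-off, and that the model overstates the contrast above 28, was seen in every scenario with re-treatment. The exact ratios rest on assumed adherence, re-treatment frequency, repeat-course length and deaths on antibiotics, and on fits without covariates. The primary analysis is unaffected. The point is worth correcting but does not threaten the trial.

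**What to change.** In section 10.2.4, Days of anti-microbial therapy, name the cut-offs and estimate Pr(Y > k) at each one directly. Either of these would do:

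- a separate mixed logistic model per cut-off, with the same covariates and site intercepts, and death on antibiotics counted as exceeding every cut-off so that the worst-category ranking is kept; or
- the partial proportional odds model already described for DOOR, with the allocation effect free to differ by cut-off.

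State that these risk ratios and differences are not read from one common odds ratio. A difference in mean days may be added only as a supplement, with mortality beside it. It drops the death ranking, so an early death would count as low exposure.

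The cost is wording and a few extra models, with no new data or patients. The downside is small: no single odds ratio summarises the outcome, and cut-off-specific estimates are somewhat less precise.
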